14.4.2 Secondary Outcome Measures

- Total, spontaneous, and traumatic ABR, and spontaneous AJBR

For total ABR, spontaneous ABR, traumatic ABR and spontaneous JABR, separate negative binomial models will be used for the second 6 months treatment period (Days 183 to 364) as well as for the complete 12-month treatment period (Days 1 to 364).

The negative binomial model for the bleed rate will include covariates for study arm, stratum, age, and race. The multiple imputations technique will be used for incomplete observation periods as described for the primary endpoints analysis. Subgroups for age and race will be analyzed as well.

For all other outcome measures, descriptive statistics will be presented for the 2 dosing regimens. Point estimates (means and medians) and their 95% CIs will be computed to include:

- Total weight-adjusted consumption of BAX 855 for each prophylactic regimen
- Overall hemostatic efficacy rating at 8 ± 1 h after initiation of treatment and at resolution of bleed
- Number of BAX 855 infusions needed for the treatment of bleeding episodes
- HJHS
- Physical domain and component scores of the SF-36
- Physical Activity Levels

In case of surgeries, descriptive statistics will be performed for the following secondary outcome measures:

- Intra-, post- and perioperative hemostatic efficacy in case of surgery (see Section [22.5.1](#) for details)
- Intra- and postoperative blood loss in case of surgery (see Section [22.5.2](#) for details)

PK parameters before randomization will be summarized descriptively over all subjects to include:

- $AUC_{0-\infty}$, IR at 15-30 minutes post-infusion, $T_{1/2}$, MRT, CL, C_{max} , T_{max} , and V_{ss}

PK parameters after 9 months will be summarized descriptively by prophylactic treatment regimen:

- $AUC_{0-\infty}$, IR at 15-30 minutes post-infusion, $T_{1/2}$, CL, C_{max} , and T_{max}
- IR over time will be displayed as boxplots for the 2 prophylactic regimens

Correlation of VWF:Ag and PK parameters will be assessed by boxplots and Spearman rank correlation coefficient.

Descriptive statistics will be used for the secondary safety outcome measures (see Section [8.4.2.2](#)):

- Occurrence of AEs and SAEs

- Changes in vital signs and clinical laboratory parameters (hematology, clinical chemistry, and lipids)
- Inhibitory antibodies to FVIII, and binding antibodies to FVIII, BAX 855, PEG, and CHO protein

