The analysis of this data involves the use of a multiple imputation technique on a transformation of this data. See Section 5.5: Handling of Missing, Unused, and Spurious Data. This is the primary analysis for the PROPEL study.

The primary analysis will be repeated as a sensitivity analysis with the following alternative imputations:

- Standard uninflated imputation (excluding regular post-PROPEL bleeds).
- Imputed bleeds with the mean inflated by 10%.
- Imputed bleeds with the mean inflated by 20%.
- Imputed bleeds with the mean inflated by 40%.
- Imputed bleeds with the mean inflated by 80%.
- Worst case bleed imputation (See Section 5.5: Handling of Missing, Unused, and Spurious Data).

The proportion of subjects with total ABR <2, spontaneous ABR <2, Spontaneous ABR = 0, spontaneous AJBR <2 and spontaneous AJBR = 0, for the second 6-month period (ObsDay 183 to ObsDay364) as well as the full 12-month period treatment period (ObsDay 1 to ObsDay 364), will be analyzed in the same manner as the primary efficacy outcome. The sensitivity analysis described above for the primary efficacy outcome, will not be applicable to the secondary efficacy outcomes.

The total ABR, injury related ABR, spontaneous ABR and spontaneous AJBR, will be analyzed using a generalized linear model fitting a negative binomial distribution with logarithmic link function for the second 6-month period (ObsDay 183 to ObsDay 364) as well as the full 12-month observation period (ObsDay 1 to ObsDay 364). Separate Negative Binomial models will be used for these two time periods. The model is to include the treatment arm assigned (low level or high level), Stratum and race as fixed effects, age at baseline as continuous covariate and the logarithm of the OPE in years as an offset. The following SAS[®] code can be used to perform the analysis:

```
Proc Genmod Data = <Dataset>;
```

```
Class <Treatment> <Strat> <Race> (param=ref ref=first);  
Model <Bleeds> = <Treatment> <PREABR> <Baseline_age> <Race> / type3  
dist = negbin link = log offset = <log_OPE>;  
lsmeans <treatment> / bylevel om CL;  
ODS OUTPUT LSMEANS = <Outdata>;  
Run;
```

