where <Dataset> refers to the input dataset, <Treatment> the assigned treatment arm, <STRAT> to the Stratum category, <Race> to the subject's race, <Bleeds> the number of bleeds during the observation period, <Baseline_age> to the subject's age at baseline, <log_OPE> the logarithm of the OPE in years and <Outdata> the output dataset containing the inferential statistics to be presented in the summary tables. Point estimates and confidence intervals obtained from the generalized linear model should be anti-logged prior to presentation.

A multiple imputation technique will be used for incomplete observation periods in the same manner as utilized for the primary analysis (See Section 5.5: Handling of Missing, Unused, and Spurious Data). This is the secondary analysis for the PROPEL study.

The potential correlation between ABR and the pre-infusion average FVIII trough levels as well as the average of the TGA trough results (lag time, time to peak thrombin generation, peak thrombin generation and ETP) will be assessed using linear regression plots with 95% confidence bands and the Spearman rank correlation coefficient for the first 6-month treatment period (ObsDay 1 to ObsDay 182), the second 6-month study treatment period (ObsDay 183 to ObsDay 364) and overall (The full 12-month period [ObsDay 1 to ObsDay 364]). As described in Section 9.1: FVIII Activity and TGA Data, FVIII trough levels will be calculated exactly to the end of the subjects' planned infusion interval; however, trough samples collected outside of ± 16 hours of the planned infusion interval, will be excluded. For TGA results, trough levels for each available visit will be included for the calculation of the average by assay if the sample was collected ± 2 hours of the planned infusion interval. Trough levels taken within ± 16 hours of the planned infusion interval will be used for this correlation test.

The following SAS[®] code can be used to perform the analysis:

```
Proc Corr data = <Dataset> Spearman;  
  Var <Parameter1>;  
  with <Parameter2>;  
  title "Correlation coefficients";  
  ODS Output = <Outdata>  
Run;
```

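### The example code for the secondary ABR model saves only arm means taken at each arm's own covariate mix, specifies no adjusted rate ratio, and fits an undefined variable in place of stratum

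*SAP*

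**What the plan says.** Both documents describe a covariate-adjusted model for the secondary bleeding-rate endpoints. Protocol 14.4.2 states: "The negative binomial model for the bleed rate will include covariates for study arm, stratum, age, and race". SAP 7.1.2 agrees: "The model is to include the treatment arm assigned (low level or high level), Stratum and race as fixed effects", with baseline age as a continuous covariate and log observation time as the offset. Protocol 7.3.1 gives the purpose, which is to compare the two regimens on total, spontaneous and trauma-related ABR.

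The example code that follows in SAP 7.1.2 contains three relevant lines:

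- the model: "Model <Bleeds> = <Treatment> <PREABR> <Baseline_age> <Race> / type3"
- the arm summaries: "lsmeans <treatment> / bylevel om CL"
- the saved output: "ODS OUTPUT LSMEANS = <Outdata>"

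The key below the code describes the saved dataset as "the output dataset containing the inferential statistics to be presented in the summary tables". It then adds: "Point estimates and confidence intervals obtained from the generalized linear model should be anti-logged prior to presentation". The same section says that incomplete observation periods are handled by multiple imputation, as in the primary analysis.

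**The concern.** A reader of the results table will see two ABRs with confidence intervals, one per arm, and will divide one by the other. Because the model is described as adjusted, the reader will take that ratio as adjusted for stratum, race and age. With these LS-means options it is not the model's adjusted rate ratio. It is that ratio multiplied by a term for how far the arms differ, by chance, in their covariates. The quantity that answers the objective, the adjusted rate ratio with its interval, is not requested in the code or named in the text.

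Separately, the MODEL line does not match the description of the model. Run literally, it would not adjust for the stratification factor as stated.

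The endpoints affected are total, spontaneous and injury-related ABR and spontaneous joint ABR, for the second six months and the full 12 months. Randomization is stratified only by pre-study regimen/ABR (SAP 2.4), so age and race are left to chance. ABR comparisons are also planned by age group and race, where arms are smaller.

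**Working it through.** The plan gives no figure for this analysis, so there is nothing to reproduce. The check compares text with code, works out what the code estimates, and sizes the difference under stated assumptions. What OM and BYLEVEL do is general knowledge of the software; the SAP does not explain the options.

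**1. Text against code (SAP 7.1.2)**

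| Item | Text | Example code |
|---|---|---|
| Stratum | fixed effect | `<Strat>` in CLASS and in the key, absent from MODEL |
| `<PREABR>` | not mentioned | in MODEL, not in CLASS, not in the key |
| Race, baseline age | included | included |
| Treatment difference | arms to be compared | no DIFF, ESTIMATE or CONTRAST |
| Adjusted treatment test | not specified | `type3` requested, table not saved |
| Saved output | inferential statistics for the tables | LS-means only |

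The name `<PREABR>` suggests a pre-study bleeding rate. If so (an inference), it would enter as one linear slope on the log rate, and the distinction between prophylaxis and on-demand treatment would drop out.

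**2. What the code estimates**

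Write β for the high-versus-low log rate ratio, g for the covariate coefficients, and x̄_H and x̄_L for the arms' covariate means.

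- With BYLEVEL OM, the log mean of arm a is b0 + b_a + g′x̄_a. The difference between arms is β + g′(x̄_H − x̄_L).
- With common margins (OM alone), both arms use the same x̄, and the difference is exactly β.

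The displayed ratio is therefore the adjusted rate ratio times exp[g′(x̄_H − x̄_L)].

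**3. Single-factor illustration (assumed effects)**

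- 10-point imbalance, bleed-rate ratio 2: exp(0.1 × ln 2) = 1.07
- 10-point imbalance, bleed-rate ratio 3: exp(0.1 × ln 3) = 1.12
- 5-year difference in mean age, 0.02 per year on the log rate: exp(0.10) = 1.11

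**4. Simulation (assumed effects)**

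The planned size is about 116 randomized 1:1 (SAP 2.3), so 58 per arm. Assumed: true rate ratio 0.50; dispersion 1, treated as known; equal follow-up; three strata in proportions 40/40/20% with log-rate effects 0, 0.5 and 1.0; age uniform from 12 to 65 with 0.01 per year; a race indicator at 25% with effect 0.4. There were 1,000 trials per scenario. The shift factor is the ratio of BYLEVEL arm means divided by the adjusted rate ratio.

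| Scenario | Shift factor, central 95% | Average ratio: adjusted / BYLEVEL | SD of log ratio: adjusted / BYLEVEL |
|---|---|---|---|
| Stratified allocation | 0.89–1.12 | 0.501 / 0.502 | 0.224 / 0.224 |
| Stratified, stronger age and race effects (0.02, 0.8) | 0.84–1.21 | 0.501 / 0.506 | 0.229 / 0.240 |
| Stratum not balanced | 0.83–1.19 | 0.499 / 0.497 | 0.224 / 0.235 |
| Subgroup, 20 per arm, stratum not balanced | 0.66–1.53 | 0.495 / 0.493 | 0.434 / 0.436 |
| No true covariate effects | 0.94–1.08 | 0.498 / 0.500 | 0.244 / 0.241 |

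With common margins, the difference in arm means equalled the adjusted log rate ratio in every simulated trial, to within 1e-15. The averages show no material bias in either version. The last row shows that estimated coefficients alone produce some shift.

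**5. Scale against sampling error**

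Assuming a mean of 1 bleed per subject and dispersion 1, the variance of the log rate is about (1 + 1)/58 per arm. So SE(log rate ratio) ≈ √(2 × 2/58) = 0.26, and the 95% interval spans a factor of about exp(±1.96 × 0.26), or 0.60 to 1.67.

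**The case against.** The strongest reply is that the adjustment has not been lost. The covariates are in the fitted model, the treatment coefficient is the adjusted log rate ratio, and `type3` gives an adjusted test. The code is offered only as something that can be used. The SAP refers layout to Output Templates that are not part of these documents and may contain a rate ratio. SAP 7.1.2 does list comparisons on ABR. It also plans a dot-and-whisker plot of ABR by arm, for which arm means with confidence limits are a reasonable descriptive input. The shift has no direction, stratification limits it for stratum, and it is small beside the sampling error in step 5. `<PREABR>` may be a naming slip that a programmer following the text would correct.

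Much of this stands. A reader might infer that the secondary ABR analysis is effectively unadjusted, or that no between-arm comparison will be reported. The documents support neither. The fitted model is adjusted, the BYLEVEL means are not the same as crude arm rates, and the content of the templates is unknown.

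What remains is narrower. The key ties the tabulated inference to a dataset holding only the arm means. The `type3` result is not saved, a p-value is not an effect estimate, and no rule is given for pooling it over imputations. The list of comparisons names no effect measure. Removing chance imbalance in the one trial that is run is the reason for pre-specifying covariates, so the absence of average bias does not dispose of the point. The mismatch over `<PREABR>` is visible on the page and needs correction whatever its cause.

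**Conclusion.** Wrong as written, for the secondary analysis only. The example code does not fit the stated model, because `<PREABR>` stands in place of stratum. The saved output does not deliver the covariate-adjusted comparison that the stated model and objective call for. The ratio of the displayed ABRs includes chance imbalance in age, race and stratum.

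The size depends on covariate effects and dispersion that the documents do not give. Under the base-case assumptions the factor is 0.89–1.12 at 58 per arm. It widens with stronger covariate effects or unbalanced strata, and most in small subgroups. This is not a claim that the treatment effect is biased: the simulations show no material average bias and, in the base case, no loss of precision. The primary chi-square test does not use this model and is unaffected.

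**What to change.** In SAP 7.1.2:

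1. Replace `<PREABR>` with `<Strat>` in the MODEL statement, so that the code matches the text, the CLASS line, the key and Protocol 14.4.2.
2. Drop BYLEVEL, so that both arms are evaluated at common covariate margins. Requesting a difference while keeping BYLEVEL would retain the imbalance.
3. Request the treatment difference with confidence limits, and send the differences table to ODS output alongside the LS-means. Without the second part the difference would still not reach the tables.
4. Pool the log rate ratio and its standard error over the imputed datasets, and only then exponentiate.
5. State in the text that the reported between-arm effect is the adjusted rate ratio with its 95% CI, with the arm ABRs shown as supporting description.

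The cost is a few code lines and one table row. No new data are needed, and the fitted model changes only in that it becomes the one already described.

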14.4.3 Exploratory Outcome Measures

Boxplots and Spearman rank correlation coefficient will be used to assess the correlation between the average of various coagulation parameters (TGA parameters: lag time, time to peak thrombin generation, peak thrombin generation, and endogenous thrombin potential [ETP] and FVIII trough levels) and ABR in the same time periods (first 6 months, second 6 months, overall).

Changes from baseline to completion/follow-up for subjects for the 2 dosing arms will be tested using the minimally importance difference threshold and the Wilcoxon sign rank test for the following PROs:

- Bleed and pain severity as measured by the Haemo-SYM questionnaire
- HRQoL as assessed using the EQ-5D and mental domain and component scores of the SF-36 questionnaire
- Health Resource Utilization

Differences in the change scores between treatment groups will be tested using the minimally importance difference threshold and the Mann-Whitney U Test for the following PROs:

- Bleed and pain severity as measured by the Haemo-SYM questionnaire
- HRQoL as assessed using the EQ-5D and mental domain and components scores of the SF-36 questionnaire
- Health Resource Utilization

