where <Dataset> refers to the input dataset, <Parameter1> the first parameter to be checked for correlation, <Parameter2> the second parameter to be checked for correlation and <Outdata> the output dataset containing the inferential statistics to be presented in the summary tables. Please note that the two variables being checked for correlation must be sorted/ranked from low to high before using the SAS procedure.

Where applicable, the 95% CI on the median will be determined using the distribution-free CI for the 50th percentile from the SAS[®] UNIVARIATE procedure.

The protocol states that for subjects that leave the PROPEL study before completing the full second 6-month period (defined as ObsDay 364), subjects may provide bleeding data for the remaining days up to the end of the full 6-month period (ObsDay 364). There were two subject cases identified which fits this description in PROPEL:

- Subjects transitioning from PROPEL to the Baxalta Continuation study before ObsDay 364.
- Subjects leaving the study before ObsDay 364 but not transitioning to another Baxalta study.

The appropriate file notes have been put in place describing this process. Details of bleed information inclusion into the PROPEL analysis (primary, secondary and exploratory) is given below.

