11. EXPLORATORY ANALYSES

The following exploratory efficacy outcome measures are discussed in Section 7.1.2: Bleeding Episodes:

- Testing for presence of correlations between various coagulation parameters and ABR.

The following exploratory efficacy outcome measures are discussed in Section 7.2: Analysis of Secondary Efficacy Outcome Measures:

- Haemo-SYM questionnaire bleed and pain severity.
- EQ-5D questionnaire.
- SF-36 questionnaire Mental domain and component scores.
- Health resource utilization.

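### The exploratory Spearman analysis against ABR gives TGA troughs two sampling windows and adds a needless sort/rank instruction that could break subject pairing if misread

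*SAP*

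**What the plan says.** The protocol (Section 14.4.3) sets the method: "Boxplots and Spearman rank correlation coefficient will be used to assess the correlation between the average of various coagulation parameters", with the coefficient computed against ABR in the same period. SAP Section 11 places it among the exploratory outcomes: "Testing for presence of correlations between various coagulation parameters and ABR".

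SAP Section 7.1.2 gives the detail for five measures (FVIII trough and four TGA parameters) over three periods (first six months, second six months, full year).

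- **FVIII window.** Troughs are calculated to the end of the planned interval, and "trough samples collected outside of ± 16 hours of the planned infusion interval, will be excluded".
- **TGA window.** Trough results are "included for the calculation of the average by assay if the sample was collected ± 2 hours of the planned infusion interval".
- **Next sentence.** "Trough levels taken within ± 16 hours of the planned infusion interval will be used for this correlation test". It names neither FVIII nor TGA.
- **Code.** "Proc Corr data = <Dataset> Spearman", with both variables read from a single input dataset.
- **Note after the code.** "the two variables being checked for correlation must be sorted/ranked from low to high before using the SAS procedure".

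Section 7.1.2 refers to Section 9.1 for the trough calculation. The correction formula and the FVIII windows are in Section 9.2, and neither section gives a window or a time correction for TGA troughs.

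**The concern.** On the windows, a programmer has two rules for the same TGA samples. The ±16 h allowance is workable for FVIII because each value is moved to the end of the interval by formula. TGA values have no such step, so applying ±16 h to them would average samples taken up to one half-life early or late as if they were troughs.

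On the sort note, Spearman's coefficient needs each subject's trough or TGA value beside that subject's own ABR. The note is mandatory, covers both variables and does not mention keeping pairs. One sort of whole records cannot in general put two imperfectly related variables both in ascending order, so a literal reader could end up sorting each column alone.

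At stake is exploratory objective 1 (Protocol 7.4, SAP 1.1.3), the relation of achieved trough and thrombin generation to bleeding. For FVIII trough, the study rationale implies an inverse relation with ABR, so separately sorted columns would also give the wrong sign.

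**Working it through.** The documents state no value for any of these correlations, so there is no planned figure to reproduce.

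**Window**

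Input: 16 h, the reported half-life that SAP 9.2 uses to justify its ±16 h limit. SAP 9.2 corrects a measured trough by the factor 2^((time after dose − interval)/half-life). The ratio of an uncorrected value to the true trough is the inverse of that factor.

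| Sample time against planned interval | Calculation | Ratio to trough |
|---|---|---|
| 16 h early | 2^(16/16) | 2.00 |
| 2 h early | 2^(2/16) | 1.09 |
| 2 h late | 2^(−2/16) | 0.92 |
| 16 h late | 2^(−16/16) | 0.50 |

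Edge to edge, that is 2.00/0.50 = 4.0-fold for ±16 h and 1.09/0.92 = about 1.2-fold for ±2 h. These ratios are for FVIII activity. The documents give no relation between FVIII activity and lag time, time to peak, peak or ETP, so they cannot be carried over to the TGA parameters.

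**Sort/rank note**

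Inputs from SAP 2.3: 48 evaluable subjects per arm (96 in all), 116 randomized, and 40% and 70% expected bleed-free, with midpoint (40 + 70)/2 = 55%. Assumptions made for the check: continuous trough, negative binomial bleed count with dispersion 0.8, and latent correlations of −0.6, −0.3, 0 and +0.3. There were 1,000 simulated trials per setting. The SAP's note can be carried out in three ways, each compared with untouched data.

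With 55% zeros (mean rho):

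| N | Latent correlation | Untouched | Each variable ranked in place | Whole records sorted | Columns sorted separately |
|---|---|---|---|---|---|
| 48 | −0.3 | −0.257 | −0.257 | −0.257 | 0.898 |
| 96 | −0.6 | −0.512 | −0.512 | −0.512 | 0.901 |
| 96 | −0.3 | −0.255 | −0.255 | −0.255 | 0.901 |
| 96 | 0 | 0.004 | 0.004 | 0.004 | 0.902 |
| 96 | +0.3 | 0.254 | 0.254 | 0.254 | 0.901 |
| 116 | −0.3 | −0.257 | −0.257 | −0.257 | 0.903 |

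Ranking in place or sorting whole records changed rho by 0.000 in every run.

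With N = 96, latent correlation −0.3 and the zero share varied:

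| Share with ABR = 0 | Untouched, mean rho | Columns sorted separately, mean (range over runs) |
|---|---|---|
| 40% | −0.269 | 0.957 (0.892 to 0.982) |
| 55% | −0.253 | 0.902 (0.790 to 0.950) |
| 70% | −0.226 | 0.800 (0.648 to 0.900) |

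Hand check: once both columns are in ascending order, rho depends only on the ties. For a continuous trough it is about √(1 − Σp³), where p is the share of subjects at each tied ABR value. Counting only the ties at zero gives √(1 − 0.4³) = 0.97, √(1 − 0.55³) = 0.91 and √(1 − 0.7³) = 0.81. These lie slightly above the simulated means, as expected when the ties at non-zero counts are left out. The true correlation does not enter the formula. With no ties at all, rho is exactly 1.

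**The case against.** The strongest reply is that the SAP does not order anyone to break pairing. It writes sorted/ranked, and its code takes both variables from one dataset, where a subject's two values share a record. Ranking, or an ordinary sort of that dataset, leaves the coefficient unchanged. That stands. A reader might infer that the plan instructs a correlation near +1 or one with the wrong sign, but the documents do not support this. It needs a further step that they never describe: detaching each column, sorting it alone and recombining. Even then rho would not reach +1 with the expected ties at zero.

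A reader might also take this to be the only planned link between achieved levels and bleeding. It is not: SAP 5.8 and 7.1.2 plan regression plots of trough and TGA against ABR, to which the sort note is not attached. A coefficient of +0.9 beside a flat or falling plot should be noticed.

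On the windows, ±2 h is the rule that names TGA, and the ±16 h sentence may only restate the FVIII rule. It would then merely repeat a limit given two sentences before, and the text does not say so; its scope is therefore open. It is also fair that samples near ±16 h should be uncommon, since Protocol 12.3 schedules trough sampling just ahead of the next dose. SAP 9.2 nevertheless allows for timing deviations, and the number of affected TGA samples cannot be known from the documents.

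**Conclusion.** Both defects are real but minor.

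The TGA window is inconsistent as written, and the choice matters because only FVIII has a time correction. The twofold and half-fold edges rest on the SAP's 16 h half-life and apply to FVIII activity. The consequence for TGA parameters is a direction of concern without a size.

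The sort/rank note adds nothing under either harmless reading and ruins the coefficient under the third, where mean rho would be about +0.80 to +0.96 for zero shares between 70% and 40%. Those figures hold only if the columns are sorted separately, and they rest on the assumed bleed-count model. The hand formula shows that the zero share does most of the work.

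The analysis is exploratory, and the primary and secondary endpoints are untouched.

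**What to change.** In SAP Section 7.1.2:

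1. Replace the unrestricted ±16 h sentence with one saying that this window applies only to FVIII troughs corrected to the end of the planned interval, and that TGA values enter the averages and the correlation only if sampled within ±2 h.
2. Delete the sort/rank note. State instead that the procedure runs on one record per subject and period, holding that subject's own average trough or TGA value and own ABR.
3. While editing, point the cross-reference to Section 9.2.

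The cost is two sentences and a section number. The one analytic downside is that TGA averages will use fewer samples than under ±16 h, and a subject with no TGA sample inside ±2 h in a period has no value for that period. Reporting the number of subjects and samples behind each coefficient would make that visible.
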